1.0 Objectives

1.1 Primary Objective:

1.1.1 - To compare postoperative pain control and quality of life in patients undergoing liver and/or pancreatic resection between those receiving thoracic epidural analgesia (TEA) versus intravenous patient-controlled analgesia (IVPCA).

1.2 Secondary Objectives:

1.2.1 - To compare postoperative/surgical outcomes between TEA and IVPCA groups.

1.2.2 - To validate survey instruments in the assessment of postoperative quality of recovery/satisfaction.

1.2.3 - To compare parameters of immunological responses between TEA and IVPCA groups.

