7.1 Primary Endpoints

7.1.1 - Pain scores (Numeric/Visual Pain Scale)

Pain score AUC within the first 48 hours will be used as the primary endpoint. The AUC for each patient will be computed using the trapezoidal method using the pain score versus time curve. The mean AUC pain scores within the first 48 hours will be compared between TEA and IVPKA groups for the primary analysis.

7.1.2 - Quality of Life

- Patients will complete a validated SF-8, Acute Recall QOL survey (preoperatively and then at approximately 24hrs after surgery) (Appendix G)
- Patients will complete a validated SF-36v2, Acute Recall QOL survey (preoperatively and then prior to discharge or at approximately 1 week after surgery – whichever is first) (Appendix H).

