8.0 Statistical Considerations

8.1 Methodology

- This is a two-arm randomized non-blinded study whose primary objectives are to compare postoperative pain scores and quality of life (QOL) scores in patients undergoing liver and/or pancreatic resection between those receiving TEA versus IVPCA. Eligible patients will be randomized in a 3:1 allocation ratio to the treatment group of TEA or IVPCA group (to represent our current institutional practice as well as to allow a more accurate determination of overall TEA failures and complications). Randomization will be stratified by the resection type (liver or pancreatic - 1:1). The randomization will be conducted by the CORE prior to surgery and after consent and registration. Pain will be assessed using a numeric/visual pain score at various timepoints. The pain scores will be averaged for each patient and be compared between TEA and IVPCA groups at specific time points as follows: pain scores for the first 6 hours after surgery, pain scores for the next 18hrs after surgery, pain scores for each subsequent 24hr period after surgery until postoperative day #5 or epidural removed, whichever occurs first. QOL will be assessed pre- and postoperatively using SF-8 and SF-36v2. These validated instruments will score 8 domains that will be reduced to two summary measures scales, Physical Component Summary (PCS) and the Mental Health Component Summary (MCS). Scoring will be performed utilizing proprietary certified scoring software from the vendor. QOL scores will be calculated and compared between the two groups of patients.
- Categorical data will be tabulated with frequency and percentages, and continuous variables will be summarized using descriptive statistics mean, standard deviation, median and range. The primary

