endpoint for pain scores is mean pain scores within the first 48 hours, computed as the AUC the pain score vs. time curve for each individual. In case there is missing data, we will compute the AUC while using last value carried forward to fill in the missing data. For primary analysis, 2-sample t-tests or Wilcoxon rank sum test will be used to compare mean pain scores within 48 hours post operation between TEA and IVPCA arms. The same methods will also be applied to compare mean pain scores at each time point between TEA and IVPCA. Linear mixed models including treatment, evaluation time, and interaction of treatment and evaluation time will be fit to determine the treatment effect on pain scale. Each pain score in PPS form will be analyzed for the primary analysis. Chi-square test or Fisher's exact test will be used to compare the binary outcomes between the two arms, which are related to effects of pain on patients' movement or mood, such as pain's influence on mobility or movement, cough or breath deeply, sleep and mood. Generalized estimating equation (GEE) regression models will be fit to estimate the treatment effects on the listed binary outcomes. Chi-square test will be used to compare the categorical items of QOL pre and post surgery between the two treatment arms, the same method will also be used to compare the changes pre-postoperative in items of QOL between the two arms as well.

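### Pain and quality of life are both primary at two-sided 0.05 with no rule linking them; the primary QOL score is not selected, and PPS scores listed as secondary are placed in the primary analysis

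*Combined protocol and SAP*

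**What the plan says.** Section 1.1.1 gives a single primary objective with two parts: "To compare postoperative pain control and quality of life in patients undergoing liver and/or pancreatic resection". Section 8.1 repeats it in the plural: "primary objectives are to compare postoperative pain scores and quality of life (QOL) scores". Section 7.1, headed as primary endpoints, has two entries. For pain (7.1.1), "Pain score AUC within the first 48 hours will be used as the primary endpoint". For QOL (7.1.2), the SF-8 is completed "preoperatively and then at approximately 24hrs after surgery" and the SF-36v2 "preoperatively and then prior to discharge or at approximately 1 week after surgery", whichever of those two later times comes first. Section 8.1 reduces each instrument to a physical (PCS) and a mental (MCS) summary.

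Section 8.2 powers pain at 92% (difference 1, SD 1.5) and an unnamed QOL score at 99% (difference 10, SD 9). Each uses a two-sided t-test at 0.05 with 105 TEA and 35 IVPCA evaluable patients.

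For analysis, 8.1 allows a t-test or a Wilcoxon test for 48-hour pain. For the QOL scores it says only that "QOL scores will be calculated and compared between the two groups of patients". It assigns chi-square tests to categorical QOL items and their changes. It also states: "Each pain score in PPS form will be analyzed for the primary analysis". The PPS appears in 7.2.2, under secondary endpoints, as a daily survey over the first five postoperative days.

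**The concern.** With two primary outcomes, a plan has to say what counts as success: either one, both, or one before the other. This plan does not. If a positive result on either could be reported as meeting the primary objective, the overall false-positive chance would exceed the 5% used for each test.

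Three further gaps leave the primary result open to choice after the data are seen, in a non-blinded trial with patient-reported outcomes:

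- The QOL score is one of four candidates at two different postoperative times, and whether the postoperative value or the change from baseline is compared is not fixed.
- 8.1 does not carry over the t-test that 8.2 uses to power that score.
- The PPS sentence brings further pain measures into the primary analysis, including scores from days 3 to 5, outside the 48-hour window.

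Two analysts following the text could therefore report different primary results.

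**Working it through.** **Inputs from 8.2.** 105 TEA and 35 IVPCA evaluable; pain difference 1, SD 1.5; QOL difference 10, SD 9; two-sided 0.05 for each. The correlation between the pain and QOL test statistics is not in the documents, so a range is assumed.

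**Step 1: the plan's own power figures.** The standard error is SD × √(1/105 + 1/35) = SD × 0.1952.

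- Pain: 1.5 × 0.1952 = 0.293; noncentrality 1/0.293 = 3.42; power 92.4% (noncentral t), against 92% stated.
- QOL: 9 × 0.1952 = 1.757; noncentrality 10/1.757 = 5.69; power 99.99%, against 99% stated.
- Enrolment: 140/(1 − 0.30) = 200, as stated.

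The power figures are sound on their own inputs.

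**Step 2: false-positive chance if either result suffices.** For pain plus one QOL score, this is 1 − P(both |Z| < 1.96) when neither has a true effect.

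| Assumed correlation | Chance of at least one false positive |
|---|---|
| 0 | 1 − 0.95² = 9.75% |
| 0.3 | 9.5% |
| 0.5 | 9.1% |
| 0.7 | 8.3% |

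If pain must be significant before QOL is tested, or if both must be significant, the error stays at or below 5%.

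**Step 3: counting the QOL candidates.** Two instruments × two summaries = four scores. The SF-8 pair is measured at about 24 hours and the SF-36v2 pair at discharge or about one week. Sections 7.1, 8.1 and 8.2 select none of them.

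**Step 4: what a pain-first order would cost.** The chance of a QOL claim is the chance that both tests are significant; if they are independent, the two powers are multiplied. QOL SD is 9.

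| True QOL difference | QOL power without the gate | Gated, independent | Gated, assumed correlation 0.7 (simulated) |
|---|---|---|---|
| 10 | 99.99% | 0.924 × 0.9999 = 92.4% | 92.4% |
| 7 | 97.7% | 0.924 × 0.977 = 90.3% | 91.5% |
| 5 | 80.7% | 0.924 × 0.807 = 74.6% | 78.6% |

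For comparison, an equal split (0.025 each) would lower pain power from 92.4% to 87.3% with the same 140 patients.

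**The case against.** The best defence is that pain already leads. Section 7.1.1 speaks of the primary endpoint in the singular, 8.2 powers pain first and adds QOL afterwards, and the hypothesis in 2.8 expects better pain control together with better satisfaction and QOL. A pain-led or joint reading is plausible, and under either there is no inflation. This stands as far as it goes: the documents do not show an inflated error rate. But the singular phrase sits under the pain subheading, and 8.1 limits it to the endpoint for pain scores. Sections 1.1.1, 7.1.2 and 8.1 still make QOL primary, and no decision rule is written.

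A reader might infer that the QOL test is undefined, or that chi-square in 8.1 contradicts the t-test in 8.2. Neither is supported. Section 8.2 names a t-test for a QOL score; the chi-square tests apply to categorical items, which are different variables. The gap is that 8.1 does not repeat the t-test and no score is chosen.

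The PPS sentence may be a slip, and the separate definition of the 48-hour AUC limits the harm. It is still a direct conflict with 7.2.2. A reader might infer large extra inflation from it, but the PPS form is not in the text reviewed here, so its pain scores cannot be counted.

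It is also fair to say that pain-first is one choice among several. A both-must-succeed rule needs no alpha split either, and has joint power of 92.4% if the tests are independent and the 8.2 assumptions hold. What is essential is that a rule be stated.

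**Conclusion.** The point holds as a gap in specification. Two outcomes are primary at full alpha with no rule joining them, the primary QOL score is not selected, and one sentence in 8.1 conflicts with the endpoint hierarchy in section 7.

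A reader might take 9.75% as this trial's false-positive rate. The documents do not support that. The range of 8.3% to 9.75% (correlations 0.7 to 0) applies only if either result may count as success and one QOL score is tested. The plan neither says this nor excludes it. The 92% and 99% power figures are not in question. The matter should be corrected before analysis because the remedy is wording alone.

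**What to change.** 1. In 8.1, reassign the PPS pain scores to the secondary analysis, in line with 7.2.2.
2. In 7.1, 8.1 and 8.2, test the 48-hour pain AUC first at two-sided 0.05 with one named test: the two-sample t-test that 8.2 powers, with Wilcoxon as a sensitivity analysis. Without this, the gate could open under one test and stay shut under the other.
3. Only if pain is significant, test one named QOL summary at two-sided 0.05 with the t-test. Name the instrument (which fixes the time point), PCS or MCS, and postoperative value or change from baseline. State in 8.2 that the difference of 10 and SD of 9 refer to that score, or replace them.
4. Call the other three QOL summaries and the item-level chi-square tests secondary.

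If the investigators prefer that both must succeed, they should write that instead; no alpha split is needed.

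The change adds no patients and leaves pain power at 92%. The price is that a QOL claim needs a positive pain result. The loss is modest at the planned QOL difference of 10 and also at 7, and about 6 percentage points at 5 if the tests are independent.

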8.2 Sample Size

- A total of 200 liver and pancreatic resection patients will be enrolled in order to achieve 140 evaluable patients. As these surgical procedures are for resection of malignancy, a proportion of patients will be identified with unresectable or metastatic disease at the time of planned resection either during initial laparoscopy or after open exploration. Those patients deemed unresectable at laparoscopy will not undergo open exploration, and thus, will be inevaluable for postoperative pain due to differences in incision type. Furthermore those patients that do undergo an open exploration but are deemed unresectable due to local or metastatic disease found intraoperatively will have markedly different prognoses compared to those that have a successful resection, which may bias their response to pain and quality of recovery and bias the questionnaire responses. Based on previous work at our and other institutions, it is expected that up to 30% of patients will not be evaluable due to various reasons, including ineligibility, patient withdrawal from the study, unresectable disease, and failure to complete or inaccurate completion of questionnaires. Based on historical information, if the difference in mean pain score between the two evaluable treatment groups of patients is 1 and the common standard deviation is 1.5, with a total of 140 evaluable patients (105 in TEA group and 35 in IVPCA group), the study will yield a 92% power to detect the difference, using a two-sample t-test at a two-sided significance level of 0.05. Furthermore, the study will have a 99% power to detect a difference of 10 in QOL score with a corresponding standard deviation of 9 using a two-sided Student's t-test with a type I error of 0.05. All statistical analyses will be performed with an intent to

treat methodology, including those patients who cross over between treatment groups.

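### Section 8.1 tests the QOL items and their changes with a chi-square that ignores answer order; this costs item-level power at moderate shifts but does not touch the PCS/MCS score comparison

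*Combined protocol and SAP*

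**What the plan says.** Section 8.1 (Methodology) makes two statements about QOL analysis.

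- Scores: the SF-8 and SF-36v2 yield 8 domains, which are reduced to the PCS and MCS summaries. QOL scores are then to be compared between arms. No test is named for this.
- Items: "Chi-square test will be used to compare the categorical items of QOL pre and post surgery between the two treatment arms". For the pre-to-post differences, "the same method will also be used to compare the changes pre-postoperative in items of QOL between the two arms as well".

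No ordinal test and no small-cell fallback is given for the items, and the coding of a change is not defined. Elsewhere the same section offers Fisher's exact test for binary pain-interference outcomes and the Wilcoxon test for pain scores.

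Section 8.2 plans "with a total of 140 evaluable patients (105 in TEA group and 35 in IVPCA group"). It powers QOL as a continuous score: "99% power to detect a difference of 10 in QOL score with a corresponding standard deviation of 9 using a two-sided Student's t-test".

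**The concern.** Items that are added up into domain scores normally run from worse to better, and a graded pre-to-post change also has a direction. A Pearson chi-square treats the categories as unlabelled boxes. A one-directional shift between arms, which is what a benefit of TEA would look like, is spread over k−1 degrees of freedom instead of being concentrated in one. A change score has up to 2k−1 levels, so both the dilution and the sparse cells get worse there.

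At stake is the item-level reading of QOL: a moderate, consistent shift in an item could be reported as no difference. There is also a specification gap. The only QOL test that 8.1 names is the chi-square on items, which is not the test used for the QOL power statement in 8.2.

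**Working it through.** **1. The plan's own figures.** With 105 and 35 patients, the noncentrality of a two-sample t-test is (difference/SD) × √(105 × 35/140) = (difference/SD) × √26.25 = (difference/SD) × 5.123.

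- Pain: 1/1.5 = 0.667 SD; 0.667 × 5.123 = 3.416; Φ(3.416 − 1.960) = 92.7%, or 92.4% with the noncentral t. Section 8.2 states 92%, so this reproduces.
- QOL score: 10/9 = 1.11 SD; 1.11 × 5.123 = 5.693; Φ(5.693 − 1.960) = 99.99%. Section 8.2 states 99%, so this is consistent.

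**2. Sparse cells.** The expected IVPCA count is 35 × pooled share. It falls below 5 when the share is under 5/35 = 14.3%. A 10% share gives 3.5; a 5% share gives 1.75.

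**3. Cost of the extra degrees of freedom.** Take a 1-df ordered test with 80% power, so λ = (1.960 + 0.842)² ≈ 7.85. Putting the same λ into a noncentral chi-square with more df gives:

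- 2 df (3 levels): 71%, a loss of 9 points
- 4 df (5 levels): 60%, a loss of 20 points
- 8 df (9 levels): 47%, a loss of 33 points

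**4. Simulation, shifted normal latent variable.** Arms of 105 and 35, two-sided 0.05, Pearson chi-square against tie-corrected Wilcoxon. Items used 3,000 runs per setting. Changes in a 5-level item (up to 9 categories, pre-post latent correlation 0.5) used 1,500. Numbers of levels, answer distributions and the correlation are assumptions, because the documents give none of them. Entries are Wilcoxon v chi-square power (%), with the loss in points; ranges run over the assumed distributions.

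| Outcome | 0.3 SD | 0.5 SD | 0.667 SD | 1.11 SD |
|---|---|---|---|---|
| 3 levels | 25–28 v 18–22 (6–8) | 59–62 v 47–53 (9–12) | 83–85 v 74–80 (6–9) | about 100 v 99.6 (<1) |
| 5 levels | 28–32 v 13–20 (12–15) | 65–66 v 39–48 (18–27) | 88–90 v 71–76 (14–19) | about 100 v 99.6–99.7 (<1) |
| 6 levels | 30 v 17 (14) | 70 v 45 (24) | 90 v 72 (17) | 100 v 99.6 (<1) |
| Change in a 5-level item | 26 v 11–12 (14) | 58–62 v 32 (26–30) | 82–87 v 55–59 (27–28) | 99–100 v 96–97 (3) |

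The largest loss in this model was 31 points (change score, 0.6 SD).

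**5. Simulation, proportional-odds shift** (4,000 runs; a second set of assumed distributions). Chi-square v Wilcoxon:

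- 3 levels: odds ratio 2.5, 62% v 71%
- 5 levels: odds ratio 2, 33% v 50%; odds ratio 2.5, 55% v 73%
- 9-level change: odds ratio 2, 25% v 53%; odds ratio 2.5, 42% v 74%

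At odds ratios of 2 to 3, the loss for a 9-level change score was 26 to 34 points; the top end depends on the assumed distribution. On the latent scale, odds ratios of 2 and 3 correspond to ln 2/1.81 = 0.38 SD and ln 3/1.81 = 0.61 SD.

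**6. Validity.** With no difference between arms, chi-square rejected in about 4 to 5% of runs. In the model of step 4, more than 20% of cells had expected counts below 5 in 95 to 100% of change tables, in 0 to 93% of 5- or 6-level tables, and almost never with 3 levels.

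**The case against.** The strongest objection is that the primary QOL comparison does not use this test. Section 8.1 states the objective in terms of QOL scores and reduces the instruments to PCS and MCS; 8.2 powers a score with a t-test. A reader might infer that the primary QOL objective itself loses 20 or 30 points of power. The documents do not support that: the chi-square sentence is confined to items and their changes. This part of the objection stands in full.

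Second, the loss is conditional. At the plan's own effect (1.11 SD) it nearly vanishes. This also stands, with one qualification: that effect is given for a score, the documents give none for an item, and it is well above the 0.667 SD assumed for pain. Moderate item shifts are therefore plausible, but they are an assumption.

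Third, order is inferred. The plan calls the items categorical, and a change could be coded as changed or unchanged, which needs no order, or as improved, same or worse. With three categories, the 3-level loss of 6 to 12 points would be the relevant one. This stands as a reason to give a range and to have the coding defined.

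Fourth, a reader might conclude that sparse cells make the test invalid. The simulations show no inflation of type I error; the harm is lost power only.

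**Conclusion.** The point holds as a cheap improvement to the item-level QOL analysis. If the items are ordered, as is very probable, chi-square is the less powerful choice against a directional shift. At 0.3 to 0.67 SD, or odds ratios of about 2 to 3, the loss is about 6 to 12 points for 3 levels, 12 to 27 for 5 or 6 levels and 14 to 34 for a multi-level change score. At 1.11 SD it is 0 to 3 points. These figures rest on 105 and 35 evaluable patients and on assumed level counts, distributions and change coding.

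No loss of power is shown for the PCS/MCS comparison, and the stated 99% is not in doubt on this ground. What can be said of that comparison is narrower: 8.1 names no test for it, so its analysis has to be inferred from the power statement in 8.2.

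**What to change.** In section 8.1:

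- For ordered QOL items and their changes, replace chi-square with a Wilcoxon rank sum test (van Elteren if stratified by resection type), or with a proportional-odds model of the postoperative answer adjusted for the preoperative answer. State how a change is coded.
- Keep chi-square, or Fisher's exact test where counts are small, for nominal or binary items.
- In the same edit, state that PCS and MCS scores are compared with the t-test assumed in 8.2, or by ANCOVA on the baseline score.

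The cost is wording and a few lines of code, with no new data and no change in sample size. The downside is that a rank or ordinal test is less sensitive to differences with no direction, such as one arm giving more answers at both extremes.

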8.2 Sample Size

- A total of 200 liver and pancreatic resection patients will be enrolled in order to achieve 140 evaluable patients. As these surgical procedures are for resection of malignancy, a proportion of patients will be identified with unresectable or metastatic disease at the time of planned resection either during initial laparoscopy or after open exploration. Those patients deemed unresectable at laparoscopy will not undergo open exploration, and thus, will be inevaluable for postoperative pain due to differences in incision type. Furthermore those patients that do undergo an open exploration but are deemed unresectable due to local or metastatic disease found intraoperatively will have markedly different prognoses compared to those that have a successful resection, which may bias their response to pain and quality of recovery and bias the questionnaire responses. Based on previous work at our and other institutions, it is expected that up to 30% of patients will not be evaluable due to various reasons, including ineligibility, patient withdrawal from the study, unresectable disease, and failure to complete or inaccurate completion of questionnaires. Based on historical information, if the difference in mean pain score between the two evaluable treatment groups of patients is 1 and the common standard deviation is 1.5, with a total of 140 evaluable patients (105 in TEA group and 35 in IVPCA group), the study will yield a 92% power to detect the difference, using a two-sample t-test at a two-sided significance level of 0.05. Furthermore, the study will have a 99% power to detect a difference of 10 in QOL score with a corresponding standard deviation of 9 using a two-sided Student's t-test with a type I error of 0.05. All statistical analyses will be performed with an intent to

treat methodology, including those patients who cross over between treatment groups.

- Patients undergoing major hepatectomy are a subset population of interest, since they are at higher risk of perioperative complications. Major hepatectomy is defined as resection of 3 or more segments of the liver, while minor hepatectomy is resection of 1 or 2 segments. With a target accrual to 200 patients and 140 evaluable patients, we anticipate enrolling 70 patients undergoing major hepatectomy. Based on our previous work it is expected that half of the 140 patients will undergo major hepatectomy. With 70 patients who undergo major hepatectomy and assuming a 3:1 randomization to the experimental arm and control arm (51 in TEA group and 17 in IVPCA group), this sample size will have 80% power to detect an effect size of 0.796 (i.e. 0.796-SD) in the mean pain scores between the two treatment arms, using a two-sample t-test at a two-sided significance level of 0.05. Two-sample t-tests or Wilcoxon rank sum test will be used to compare mean pain scores within 48 hours postoperatively between TEA and IVPCA arms.

9. Data and Protocol Management

After obtaining informed consent, patients will be registered by an Anesthesia/Surgery Research Nurse, who will register them on the MDACC computerized Protocol System. The PI, [name], and [name] at Mayo Clinic College of Medicine will analyze the data once the study is closed. Only Limited Data Sets (LDS) will be sent to [name] at Mayo Clinic College of Medicine, however, Mayo Clinic will not participate in the analysis or in any part of the study. LDS is Protected Health Information that excludes the sixteen (16) direct identifiers listed in the U.S. Department of Health and Human Services Health Insurance Portability and Accountability Act (HIPAA). A Data Use Agreement will be used to send the data to [name]. All data obtained will be de-identified after the conclusion of the study.

10. Data Safety and Monitoring Board

This study will be monitored by The Data Safety and Monitoring Board (DSMB), through routine reviews and/or institutional audits. The DSMB reports to the President, or his designee, as the on-campus representative of The University of Texas Board of Regents. It oversees the data and patient safety issues for randomized Phase III clinical trials that originate at UTMDACC; that are coordinated or analyzed by UTMDACC and are not being monitored by any other DSMB; or has been designated as the DSMB for any trial at the request of the IRB, the CRC, or institution. The primary objectives of the DSMB are to ensure that patients' rights pertaining to participation in a research study are protected, and that patients' interests are prioritized over the interests of the scientific investigation. Responsibilities include:

- (a) **Review interim analyses of outcome data after 60 evaluable patients are enrolled (prepared by the study statistician or other responsible person at the time points defined in the study) approved by the IRB and additional time points as determined by the DSMB, and to**

recommend, if necessary, whether the study needs to be changed or terminated based on these analyses;

- (b) Determine whether, and to whom, outcome results should be released prior to the reporting of study results;**
- (c) Review interim toxicity data and efficacy of treatment;**
- (d) Review major research modifications proposed by the investigator or appropriate study committee prior to implementation (e.g., termination, dropping an arm based on toxicity results from the study or results of other studies, increasing target sample size).**

The DSMB consists of not more than 15 members (including the Chair) as recommended by the President, or his designee, for each fiscal year. The committee includes physicians, statisticians and lay member(s), and will be selected based on their experience, reputation for objectivity, absence of conflicts of interest (or the appearance of the same), and knowledge of good clinical trial methodology. The committee meets 5 times per year, and may schedule additional meetings if needed.

11. Confidentiality

- This study will be conducted in accordance with all applicable privacy laws, rules and regulations. The Principal Investigator will take steps to guard against any loss of confidentiality. Only the Principal Investigator, Study Co-Chairs, and the authorized research team will have access to the identifiable information from this study.

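### Quality of life is a primary objective, but no stated QOL analysis adjusts for the preoperative score or resection type, which gives up precision at no saving

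*Combined protocol and SAP*

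**What the plan says.** Section 1.1.1 sets the primary objective: "To compare postoperative pain control and quality of life in patients undergoing liver and/or pancreatic resection". Section 8.1 repeats this, describing a study "whose primary objectives are to compare postoperative pain scores and quality of life (QOL) scores". Section 7.1.2, under Primary Endpoints, lists two instruments. The SF-8 is given preoperatively and at about 24 hours. The SF-36v2 is given preoperatively and again before discharge or at about one week, whichever is first. Section 8.1 reduces them to two summary scales, PCS and MCS, so there are four candidate summary scores.

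On analysing those scores, 8.1 says only: "QOL scores will be calculated and compared between the two groups of patients". It names no test, covariate, lead score or time point. The QOL methods it does name are for items: "Chi-square test will be used to compare the categorical items of QOL pre and post surgery between the two treatment arms", and "the same method will also be used to compare the changes pre-postoperative in items of QOL between the two arms". A test for a QOL score appears only in the power statement of 8.2: "difference of 10 in QOL score with a corresponding standard deviation of 9 using a two-sided Student's t-test".

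On the design, 8.1 states: "Randomization will be stratified by the resection type" (liver or pancreatic). No analysis in the plan includes that factor. The mixed model in 8.1 is for the pain scale, and the GEE models are for binary effects of pain on movement and mood.

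**The concern.** The plan collects a preoperative value of each QOL instrument and stratifies the randomisation by resection type, yet the stated analyses adjust for neither. The 3:1 allocation leaves 35 evaluable IVPCA patients, and that small arm governs the precision of the QOL comparison. If the preoperative score predicts the postoperative one, adjusting for it narrows the interval without another patient or form. If liver and pancreatic patients differ in QOL, a test that ignores the stratum overstates its own standard error. What is at stake is the width of the confidence interval for a primary objective and the power for differences smaller than the planned 10 points.

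**Working it through.** **Inputs from 8.2:** 105 TEA and 35 IVPCA evaluable patients, difference 10, SD 9, two-sided alpha 0.05, stated power 99%. **Assumed:** the pre-post correlation r, taken as 0.3, 0.5 and 0.7, with 0 as a check, and the liver-pancreas gap in mean score. The documents give neither.

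**1. The plan's own figure.** SE = 9 × √(1/105 + 1/35) = 1.757. The noncentrality is 10 / 1.757 = 5.69 on 138 df, and the power is 99.99%. The stated 99% is met.

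**2. Unadjusted precision.** Half-width = t(0.975, 138) × 1.757 = 1.977 × 1.757 = 3.47 points. The difference detectable with 80% power is 4.96 points.

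**3. With baseline adjustment, SD 9 read as the postoperative SD.** Residual SD = 9 × √(1 − r²), with 136 df (one each for baseline and stratum). The stratum is given no effect here. The last column uses a 5-point difference, half the planned one, which is an assumption and not in the documents.

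| Analysis | Residual SD | 95% half-width | Detectable at 80% power | Power for 5 points |
|---|---|---|---|---|
| Unadjusted | 9.00 | 3.47 | 4.96 | 81% |
| r = 0.3 | 8.59 | 3.31 | 4.73 | 84% |
| r = 0.5 | 7.79 | 3.01 | 4.29 | 90% |
| r = 0.7 | 6.43 | 2.48 | 3.54 | 98% |

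The equivalent gain in sample size is 1/(1 − r²), that is 1.10, 1.33 and 1.96. Power for 10 points exceeds 99.9% in every row. At r = 0, a simulation of 10,000 trials gave a mean half-width of 3.48 adjusted against 3.47 unadjusted.

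**4. SD 9 read instead as the SD of the change score.** With equal pre and post SDs, the residual SD is 9 × √((1 + r)/2). The half-width falls from 3.47 to 2.80, 3.01 or 3.20 at r = 0.3, 0.5 or 0.7. The direction is the same.

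**5. Leaving out the stratum.** Take equal strata and a total variance of 81. A gap d between liver and pancreatic means contributes d²/4 to that variance. Stratified allocation removes this part from the true variance of the arm difference, but the t-test still counts it. The ratio of true to reported SE is √((81 − d²/4)/81), and the type I error is 2 × [1 − Φ(1.96 / ratio)].

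- d = 3: √(78.75/81) = 0.986, type I error about 4.7%.
- d = 5: √(74.75/81) = 0.961, type I error about 4.1%.

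The unadjusted test is therefore mildly conservative.

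**The case against.** The strongest reply is that a power formula is not an analysis commitment. For QOL the t-test appears only in 8.2, and 8.1 is silent on how PCS and MCS will be compared. A reader might infer that the sponsor has chosen an unadjusted analysis and ruled out a better one. The documents do not go that far. This part stands: the plan names no adjustment, but it does not exclude one.

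It is also fair to say that adjustment here improves efficiency and corrects no error. At the only QOL difference the plan names, power is above 99.9% either way, and 3.47 points is already about a third of that difference. The gain depends on a correlation that the documents do not supply. At r = 0.3 it is only 0.16 points of half-width, and nothing in the documents shows how well a preoperative score predicts one taken 24 hours or a week after major resection. All of this stands as a limit on size. It is not a reason to leave the adjustment out, because at r = 0 the cost is negligible.

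It can be said, too, that the plan already uses the preoperative data by comparing pre-post changes in items. It does, but only item by item with chi-square, which does not adjust PCS or MCS. Nor would an unadjusted change in the summary score be a safe substitute. With postoperative SD 9 and equal pre and post SDs, its power for 5 points is 67%, 81% and 95% at r = 0.3, 0.5 and 0.7, against 84%, 90% and 98% for ANCOVA.

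Finally, with four summary scores and none designated, a reader might infer an inflated false-positive rate. That would need a rule claiming success on any one score, and the plan states no such rule.

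**Conclusion.** The point holds as one of lost precision. No stated QOL analysis adjusts for the preoperative SF-8 or SF-36v2 score or for resection type, though both are in hand. Under the postoperative reading of SD 9, baseline adjustment would cut the half-width from 3.47 points by 0.16, 0.46 or 0.99 points at assumed correlations of 0.3, 0.5 or 0.7, and by essentially nothing at 0. Omitting the stratum costs little: a type I error of about 4.7% to 4.1% instead of 5% for assumed gaps of 3 to 5 points.

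A reader might go further and infer a biased comparison or an underpowered one. The documents support neither. Randomisation protects the unadjusted comparison, and the 99% claim reproduces from the plan's own inputs. That 8.2 does not say which score and time point it powers is a gap in detail, best closed in the same edit, and does not carry the point by itself.

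**What to change.** In 8.1, state that postoperative PCS and MCS will be compared between arms by ANCOVA with terms for arm, the preoperative score of the same scale and resection type as stratified at randomisation, reporting the adjusted mean difference with its 95% confidence interval. In the same edit, the sponsor should state in 8.2 which summary score and time point the power statement refers to, and whether SD 9 belongs to a postoperative value or a change. With the preoperative score in the model, either outcome gives the same treatment estimate, so that last choice affects only how SD 9 is read.

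The cost is an amendment to 8.1 and 8.2. It needs no patients, visits or forms beyond those already planned, and the sample size is unaffected. The model does need a preoperative score for each patient, so the amendment should also say how a missing one is handled.
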